Feasibility will be assessed through intervention adherence, recruitment, participation, and completion rates. Acceptability will be assessed using the Client Satisfaction Questionnaire – 8 post-treatment; ACT for aphasia will be considered acceptable if the group mean is \geq 28 for the second cohort. As a secondary aim, preliminary effect sizes will also be estimated on pre-post measures of successful communication participation, psychological distress, and quality of life, along with point estimates and standard deviations to inform power analyses for a Stage II efficacy trial.

Study Design & Methods

Participant assignment: given the early phase of this research and the lack of control conditions or groups, there will be no random assignment. Participants will be enrolled in the study as they are referred and found to be eligible, with the first five participants being enrolled in the first study cohort during year 1 while the remainder of participants will be enrolled in the second cohort across years 1 and 2.

Screening procedures:

We will partially assess eligibility prior to informed consent, and finalize screening for eligibility after informed consent via interview and standardized assessments.

Pre-treatment assessments:

Participants will be assessed with a primary outcome measure (the Client Satisfaction Questionnaire-8) and several secondary outcome measures (screening questions, the Communication Participation Item Bank, the Aphasia Communication Outcome Measure-ACOM, the Stroke and Aphasia Quality of Life, the Acceptance and Action Questionnaire – ABI, the Kessler K6 non-specific distress scale, the Acceptance and Action Questionnaire II, the Modified University of Washington Resilience Scale (added for the second study cohort only), and the Comprehensive aphasia test).

Intervention description: the ACT for Aphasia treatment manual will be a 10-session intervention created by modifying an existing ACT manual provided by [name]. To meet the specific needs of stroke survivors with aphasia, ACT will be modified in two main ways.

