## 4.4. Statistical Design and Power.

The purpose of this overall research agenda is to improve communication participation, psychosocial adjustment, and quality of life (QoL) for stroke survivors with aphasia by developing an effective new integrated language and counseling, *Act for Aphasia*. At this preliminary research stage, our primary goals are to develop and pilot this intervention, laying the groundwork for a subsequent larger-scale efficacy trial. Therefore, in **Aim 1**, we will engage a stakeholder advisory board to develop and revise the treatment manual. In **Aim 2a** we will establish primary outcomes of **acceptability** and **feasibility** of ACT for Aphasia. In **Aim 2b** we will estimate preliminary effect sizes on secondary outcome measures to inform power analyses for a subsequent randomized control trial.

Methods for Determining Intervention Acceptability. Acceptability will be assessed using the Client Satisfaction Questionnaire − 8. It consists of 8 questions rated on a 4-point scale (summed scores range from 8 to 32). Participants will be given these questions at the end of follow-up assessment with an independent assessor. High scores indicate high satisfaction. We will consider *Act for Aphasia* to be acceptable if the group mean ≥28, a benchmark based on previous stroke rehabilitation work by project consultant [name].

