**Initial estimates of treatment effects.** We will assess change on two types of secondary outcome measures, ones that measure mechanisms of treatment action, and ones that measure functional outcomes. Assessments that measures mechanisms of treatment action will consist of the Acceptance and Action Questionnaire II,  which measures general psychological flexibility, the Acceptance and Action Questionnaire – ABI,  which measures psychological flexibility in relation to acquired brain injury, and the Values Tracker,  which measures values engagement. Functional outcome measures will consist of the K6,  which measures psychological distress, the Stroke and Aphasia Quality of Life – 39,  which measures QoL, the Aphasia Communication Outcome Measure,  which measures self-reported communication efficacy, and the Communication Participation Item Bank,  which measures communication participation. For these measures, we will calculate pre- to post-treatment changes by calculating standard effect sizes (Cohen's *a*). These functional outcome measures will serve as primary outcome measures in planned Stage II efficacy research, should ACT for aphasia appear promising (see "Use of pilot data to inform development of a full-scale efficacy trial" below).

**Statistical Approach.** Primary outcomes will assess intervention feasibility and acceptability. Secondary outcome measures will provide initial estimates of participate response and variability. We will report means and standard deviations for continuous variables and frequencies and proportions for categorical variables, with 95% confidence intervals for both types of variables. As a preliminary check on treatment validity, we will explore the association between changes on mechanistic measures (i.e., psychological flexibility, values engagement) and secondary measures of functional outcomes (e.g., QoL) via multi-level regression models (please see Clinical Trials Information Section 4.4 for additional information). We will also examine whether biological sex exerts an effect on any primary acceptability and feasibility outcomes measures via appropriate statistical tests (e.g., a two-sample *t* test or nonparametric alternatives, depending on data distributions).

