**Sample size justification.** Total sample size (N=21; N=5 for Cohort 1 and N=16 for Cohort 2) is considered to be realistic based on level of project staffing and previous experience recruiting PWA in the Pittsburgh area. The sample size for Cohort 1 was chosen to provide preliminary feedback for the first version of the treatment manual, while also making sure the size of the SAB stays manageable over time (should all five participants decide to join the SAB when invited, this would bring the total number of SAB members to nine). The sample size for Cohort 2 is considered adequate for providing a precise estimate of treatment acceptability. This is because even with an overly conservative attrition rate of 25%, final completion rates would still be N=12, which meets minimum recommendations for providing reasonably precise confidence intervals for continuous variables.

Use of pilot data to inform development of a full-scale efficacy trial. The determination of whether a full-scale trial is warranted will be based on whether ACT for Aphasia meets our criteria for feasibility and acceptability (Aim 2a) and whether it appears to be promising in terms of promoting functional recovery (Aim 2b). We will also examine within-group effect sizes (with 95% confidence intervals to reflect uncertainty regarding the reliability of the treatment effects sizes for planning a subsequent trial). Should ACT for Aphasia appear promising, these data will be used to inform the power analysis to determine sample size for a subsequent efficacy trial.

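### Pre-post Cohen's d for Stage II planning has no stated small-sample correction or standardiser; scaled by the baseline or change SD, it runs 5.4% to 7.5% high at 16 to 12 completers

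*SAP*

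**What the plan says.** The study is a single-group pre-post pilot: the protocol (Study Design & Methods) states that "given the early phase of this research and the lack of control conditions or groups, there will be no random assignment". For the mechanism and functional measures, SAP 4.4 (Initial estimates of treatment effects) says "we will calculate pre- to post-treatment changes by calculating standard effect sizes" and names Cohen's d with a citation. The letter is printed as an a in the extracted text, and I read it as d.

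The purpose is explicit. Under Aim 2b, "we will estimate preliminary effect sizes on secondary outcome measures to inform power analyses for a subsequent randomized control trial". The closing paragraph of SAP 4.4 adds that, if the treatment looks promising, "these data will be used to inform the power analysis to determine sample size for a subsequent efficacy trial". The feasibility paragraph would compare the resulting sample size with recruitment when choosing between one site and several.

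The plan also promises material that bears on this point. SAP 4.4 has "We will also examine within-group effect sizes (with 95% confidence intervals to reflect uncertainty regarding the reliability of the treatment effects sizes". The protocol (Study Objectives, Aim 2) offers the effect sizes "along with point estimates and standard deviations to inform power analyses for a Stage II efficacy trial", and the Statistical Approach paragraph promises means and SDs for continuous variables.

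The text provided does not state a small-sample correction, the SD that forms the denominator, the SD of change, the pre-post correlation, or which cohort or cohorts contribute to the effect sizes.

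**The concern.** There are two separate gaps.

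- **Small-sample bias.** Uncorrected d overstates the true standardised effect in expectation, and the overstatement is not negligible at the planned number of completers. It pushes every measure away from zero.
- **Undefined scale.** With paired data, Cohen's d is not one quantity. The mean change may be divided by the baseline SD, by an average of the pre and post SDs, or by the SD of the change scores. Two analysts following the SAP to the letter could report different values from the same data.

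The stake is Stage II planning, which is the stated purpose of Aim 2b. A planned sample size varies with the inverse square of d, so an error in d is magnified there. A confidence interval expresses sampling uncertainty. It does not remove bias from the point estimate, and it sits on whatever scale the estimate has.

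**Working it through.** **Inputs from the documents.** "Total sample size (N=21; N=5 for Cohort 1 and N=16 for Cohort 2" and a 25% attrition allowance. The plan's own figure reproduces: 16 × (1 − 0.25) = 12 completers.

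**Assumed inputs.** The pre-post correlation r is not in the documents, so a range is shown. Normal data are assumed throughout, and equal pre and post SDs in steps 2, 4 and 5.

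**1. Bias with the baseline or change SD.** The Hedges factor is J(df) = Γ(df/2) / [√(df/2) · Γ((df − 1)/2)], with df = n − 1. The expected value of uncorrected d is the true value divided by J.

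| n | J | 1/J | d runs high by |
|---|---|---|---|
| 12 | 0.930 | 1.075 | 7.5% |
| 14 | 0.941 | 1.063 | 6.3% |
| 16 | 0.949 | 1.054 | 5.4% |
| 21 (pooled, all complete) | 0.962 | 1.040 | 4.0% |

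A simulation with 400,000 replicates agrees for both denominators: 1.075 at n = 12, and 1.053 to 1.054 at n = 16.

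**2. Bias with an averaged pre/post SD.** The bias is smaller because two variances contribute. Simulated values are 4.4% (r = 0.5) and 5.8% (r = 0.8) at n = 12, and 3.2% and 4.2% at n = 16.

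**3. How large this is.**

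- Beside sampling error: an observed change-SD d of 0.50 has a 95% interval of −0.11 to 1.09 at n = 12 and −0.03 to 1.01 at n = 16. The correction moves 0.50 to 0.50 × 0.930 = 0.465, or to 0.50 × 0.949 = 0.475. The shift is 0.035 or about 0.026, against a half-width of (1.09 + 0.11)/2 = 0.60 at n = 12.
- In planned size: putting the expected uncorrected d into a sample size formula multiplies the size by J², which is 0.930² = 0.865 or 0.949² = 0.901. For an assumed true effect of 0.40 (two-sample t test, two-sided 5%, 80% power), 100 per arm becomes 86 or 90. This substitutes the expected d; it is not the expected shortfall over repeated pilots.

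**4. Scale.** The variance of change is 2(1 − r) times the baseline variance. So d on the change SD divided by d on the baseline SD equals 1/√(2(1 − r)).

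| assumed r | 0.2 | 0.5 | 0.7 | 0.8 | 0.9 |
|---|---|---|---|---|---|
| ratio | 0.79 | 1.00 | 1.29 | 1.58 | 2.24 |

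The ratio reaches 1.6 only at r = 1 − 1/(2 × 1.6²) = 0.805.

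**5. What Stage II needs depends on its analysis.** Take a baseline-SD effect of 0.40, r = 0.8, two-sided 5% and 80% power.

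| Stage II analysis | effect to enter | per arm |
|---|---|---|
| post-treatment score | 0.40 | 100 |
| change score | 0.40/√(2 × 0.2) = 0.632 | 41 |
| ANCOVA on baseline | 0.40/√(1 − 0.8²) = 0.667 | 37 |

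Entering 0.632 for a post-score comparison would plan far too few participants. Entering 0.40 as if it were already on the change-score scale would plan 100 where 41 suffice, a ratio of 100/41 ≈ 2.4.

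**The case against.** The strongest reply is that little harm follows. The estimates are secondary and preliminary, and the bias is far smaller than the uncertainty that the planned 95% intervals will show. Means and SDs are also promised. If they are given at each time point, the baseline-SD effect is simply the mean change divided by the baseline SD. If a change-SD d is also reported, the SD of change is the mean change divided by that d, and r = (s₁² + s₂² − s_change²)/(2·s₁·s₂). This works when all figures come from the same completers and the mean change is not near zero. The sponsor also holds the raw data.

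Most of this stands. It limits the scale problem to one of clarity, and I do not claim that a reported d could not be converted. It does not answer the bias, which a one-line multiplication removes. It also leaves readers to reconstruct the SD of change and r, which the plan does not name, although a change-score or ANCOVA design needs one of them.

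A reader might infer more: that the effect sizes will be wrong by 1.6-fold or more, that Stage II will therefore be too small, and that only the baseline-SD effect should be carried forward. The documents do not support this. They give no r; 1.6-fold needs r of about 0.80 or more, and below 0.5 the direction reverses. They also give no Stage II analysis model, and the change-SD value is the right input for a change-score comparison.

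Nor can it be said that the sponsor has no correction or standardiser in mind. The effect size carries a citation that is not available here, part of the SAP was removed before review, and the SAP refers to further detail elsewhere. The supportable statement is that neither is given in the text provided.

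**Conclusion.** The concern holds as an analysis choice worth tightening.

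- **Bias.** At 12 to 16 completers, uncorrected d runs 7.5% to 5.4% high with the baseline or change SD. It runs about 3% to 6% high with an averaged SD at r of 0.5 to 0.8, and about 4% high if all 21 complete and are pooled. These figures assume normal data. The bias is minor beside sampling error, but always in the same direction.
- **Scale.** The unnamed standardiser leaves a factor between 0.79 and 2.24 over assumed r of 0.2 to 0.9, with equal pre and post SDs. Misuse could make Stage II too small or too large. This is a risk of misreading, not a demonstrated error, and the promised means and SDs reduce it.

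The primary acceptability and feasibility outcomes are unaffected.

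**What to change.** In SAP 4.4 (Initial estimates of treatment effects), replace Cohen's d with a Hedges-corrected effect size and state the following.

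- The standardiser, for example the baseline SD.
- The correction J(df) with df = n − 1, computed at the actual number of completers for each measure rather than from fixed constants. This df suits the baseline or change SD; an averaged SD would need its own df.
- Which cohort or cohorts contribute, since this sets n.
- A 95% confidence interval suited to paired data.
- The SD of change and the pre-post correlation for each measure.

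Stage II planning can then use the scale that matches its own analysis, whether post-score, change-score or ANCOVA. The SAP should not require that only the baseline-SD effect be carried forward.

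The cost is a few sentences and a few lines of code, with no new data. The reported effect sizes become slightly smaller.

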First, the intervention will include modified language and communication supports to address the unique communication challenges faced by people with aphasia that could impede engagement with ACT content. Multi-modality communication supports will be provided by the treating clinician (e.g., writing out key words to support verbal content, summarizing and providing repetitions, providing session summaries to review between sessions). Manual creation will follow existing practice recommendations for modifying counseling interventions for PWA (e.g., simplifying language and increasing use of visual metaphors) which will be reviewed by the SAB.

Second, ACT will be further augmented via individualized language compensation training and a focus on identifying and addressing communication-based barriers to life participation. Language training will focus on active compensatory strategies such as self-cuing, use of alternative modalities (gesture, writing), and use of commonly available technology (e.g., smartphone dictionaries, text-to-speech). The details of this language compensation training will also be determined based on input from the Stakeholder Advisory Board (SAB), and will be revised after reviewing performance and interview feedback from each successive cohort.

Post-treatment phase:

In this phase, participants will be given the same series of assessments received in the pre-treatment phase. In addition, they will have an interview to provide feedback about the intervention and suggestions for improvement.

Post-treatment interviews providing feedback for protocol revision will be administered by trained study staff within three weeks of treatment completion.

Interviews will use a semi-structured, ethnographic interview approach and be video-recorded. These interviews will ask specific questions about the participant's experience and perspective regarding each functional domain of the intervention (i.e., the "Open Up," "Be Present," and "Do What Matters" components of ACT and the individualized language compensation training), and will be asked for suggestions and improvements about the specific content and techniques employed.

Eligibility Criteria

Inclusion Criteria:

Participants will be age 18 or older with an existing diagnosis of aphasia subsequent to left hemisphere stroke as confirmed by a) registry referral sources or b) personal copies of medical records (provided by the participant following informed consent).

Exclusion Criteria:

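### The SAP does not say how change enters its multi-level mechanism model, and the usual random-intercept fit to raw scores does not estimate the association between changes

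*SAP*

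**What the plan says.** The Statistical Approach paragraph of SAP section 4.4 sets the target: "we will explore the association between changes on mechanistic measures" "and secondary measures of functional outcomes (e.g., QoL) via multi-level regression models". It introduces the analysis with the words "As a preliminary check on treatment validity".

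The paragraph on initial estimates of treatment effects lists three mechanism measures (AAQ-II, AAQ-ABI, Values Tracker) and four functional outcomes (K6, SAQOL-39, ACOM, CPIB). It treats change as a single pre-to-post difference: "For these measures, we will calculate pre- to post-treatment changes by calculating standard effect sizes". The Protocol, under the post-treatment phase, agrees: "participants will be given the same series of assessments received in the pre-treatment phase". It describes no mid-treatment or later wave. The Values Tracker ("which measures values engagement") is missing from the Protocol's assessment list, and neither document gives its schedule.

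On the model, the available text states no fixed effects, pre/post term, centring or random-effects structure. It refers onward: "please see Clinical Trials Information Section 4.4 for additional information". The SAP text available for review carries that section number and adds nothing on the model, but part of the SAP was removed before review.

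**The concern.** The target is a relation between two changes. With one score before and one after treatment, each participant contributes one change per scale. For one mechanism-outcome pair, a model of those changes has one row per person, so a person-level random effect cannot be told apart from the residual. An analyst told to use a multi-level model for that pair would most naturally turn to the two raw scores per person with a random intercept.

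The slope of that model is a weighted blend of three things:

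- the within-person association, which is the target;
- the stable between-person correlation (less flexible people may be more distressed before any treatment);
- without a pre/post term, the average movement of both scales over the same weeks. With no control group, that movement may have nothing to do with the mechanism.

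The pilot could then report support for the ACT mechanism although participants whose flexibility improved did no better in function than the others.

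**Working it through.** **1. Sample sizes.** The plan's completer figure reproduces: 16 × (1 − 0.25) = 12. The check uses n=12 (Cohort 2 completers), n=16 (all of Cohort 2) and n=21 (both cohorts). The documents give no figure for the mechanism model itself.

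**2. Assumed inputs, none from the documents.** Each scale has variance 1 at each occasion and stability 0.7, so stable variance is 0.7 and occasion variance 0.3. Between-person correlation is 0.6. Both scales improve on average by 0.5 SD. The true association between individual changes is zero. Tests are two-sided at 0.05; the SAP states no alpha for this analysis.

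**3. What each model estimates.** For each scale let S = (pre + post)/√2 and D = (post − pre)/√2. Then:

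- Var(S) = 2 × 0.7 + 0.3 = 1.7
- Cov(S of mechanism, S of outcome) = 2 × 0.7 × 0.6 = 0.84
- Var(D) = 0.3, and Cov(D of mechanism, D of outcome) = 0
- the squared mean of D is 0.5²/2 = 0.125

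The random-intercept slope is b = (λ × 0.84 + c) / (λ × 1.7 + v), where λ is the residual variance of D divided by that of S.

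- No pre/post term: c = 0.125 and v = 0.3 + 0.125 = 0.425. At b = 0.404 the residual variances are 0.425 − 2(0.404)(0.125) + 0.404²(0.425) = 0.393 and 1.7 − 2(0.404)(0.84) + 0.404²(1.7) = 1.299, so λ = 0.303. Then b = (0.2545 + 0.125)/(0.515 + 0.425) = 0.404.
- With a pre/post term: c = 0 and v = 0.3. At b = 0.284 the residual variances are 0.324 and 1.360, so λ = 0.238. Then b = 0.200/(0.405 + 0.3) = 0.284.
- Change on change: b = 0/0.3 = 0, which is the truth.

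**4. False-positive rates by simulation** (1,500 trials per cell, inputs as in step 2):

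| Model | n=12 | n=16 | n=21 | Mean slope |
|---|---|---|---|---|
| Random intercept, raw scores | 50% | 64% | 75% | about 0.40 |
| Same, plus pre/post term | 29% | 36% | 43% | about 0.29 |
| Change on change | 5.0% | 4.8% | 4.5% | about 0 |

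The simulated slopes agree with step 3. The bias does not shrink as n grows, so the error rate rises.

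**5. Sensitivity (stability 0.7 throughout).**

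- Correlation 0.5, shift 0.5 SD, at n=12/16/21: raw-score model 44.5% / 55.7% / 66.7%; with pre/post term 22.5% / 27.4% / 31.9%; person-mean-centred without a pre/post term 15.3% / 21.0% / 25.5%; centred with a pre/post term 4.5% / 4.9% / 3.7%. Both corrections are needed.
- Correlation 0.5, shift 0.8 SD, n=21: raw-score model 92%.
- Correlation 0, shift 0.5 SD: raw-score model 15% to 20%.
- Correlation 0, shift 0: raw-score model 6% to 8%.

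**6. Two occasions suffice under the right model.** In a test data set, the two-occasion mixed model with person mean, centred score and pre/post term gave a within-person slope of 0.492, the same as change on change.

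**7. Precision.** The 95% half-width for a correlation near zero is tanh(1.96/√(n − 3)): 0.57 at n=12, 0.50 at n=16 and 0.43 at n=21. Three mechanism measures by four outcomes make 12 pairs. If all were tested at 0.05 and independent, the chance of at least one false positive would be 1 − 0.95¹² = 0.46.

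**The case against.** A reader might infer that two measurement occasions make the planned analysis impossible. That does not hold: step 6 shows that a correctly specified two-occasion model recovers the target.

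A reader might also infer that the SAP prescribes the biased model. It does not. It writes no model terms, and it states the target as an association between changes, which a raw-score regression departs from. The high rates belong to one common way of carrying out the sentence. Detail may also exist in the part of the SAP that was not available.

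Nor is the raw-score fit the only multi-level option. Standardised changes on all four outcomes, stacked within person, give four rows each and an estimable random intercept. Under the inputs of step 2, plus an assumed 0.4 correlation of occasion errors among outcomes, that model was falsely positive in 3.8%, 4.8% and 5.7% of trials at n=12, 16 and 21. The documents do not say that it is intended.

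The rates rest on assumed inputs and range from near nominal to above 90%. The Values Tracker may be collected more than twice. The analysis is labelled exploratory, and the SAP's criteria for a full-scale trial are feasibility, acceptability and functional promise, without this association.

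All of this stands, and it limits the point to model specification at low severity. It does not remove it: the text as available permits a fit that misses its own stated target, and a better one needs no new data.

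**Conclusion.** The concern holds as a specification problem of minor severity. For a single mechanism-outcome pair, the usual random-intercept regression of raw scores does not estimate the association between changes. With no such association, it is falsely positive in about 50% of trials at n=12 and 64% at n=16, or 29% and 36% with a pre/post term, against about 5% for change on change. This rests on between-person correlation 0.6, stability 0.7 and a 0.5 SD shift, all assumed. Only with neither correlation nor shift does the raw-score model come close to nominal.

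Even the corrected analysis cannot show mechanism. Both changes cover the same interval, so temporal order is unknown. Shared occasion error also inflates the result: an assumed within-occasion error correlation of 0.3 made change on change significant in 18.6% of trials at n=16. The primary outcomes, the effect sizes and the sample size are unaffected.

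**What to change.** In the Statistical Approach paragraph, replace the general reference to multi-level models with one of two statements:

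- For each pre-named mechanism-outcome pair, regress post-minus-pre change in the outcome on post-minus-pre change in the mechanism measure, with an intercept and one row per participant. Report the slope with its 95% confidence interval.
- If a mixed model is kept, enter the person mean and the person-mean-centred mechanism score, add a pre/post term and a random intercept, and interpret only the within-person coefficient.

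Name the pairs in advance, state the Values Tracker schedule, and add a sentence that the result is an exploratory association which shows neither temporal order nor mechanism.

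The change is to wording only and needs no new visits or data. The price is a wide interval (step 7), because differences between people no longer feed the estimate. That width reflects what a pilot of this size can tell about the question.
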